***A Study to Measure Pain Perception Following De-
Epithelialized Free Gingival Graft Harvesting.***

Study Protocol & Statistical Analysis Plan

NCT03895476

January 23, 2023

[name], MS, Principal Investigator

University of Alabama at Birmingham

Birmingham, AL 35294

A Study to Measure Pain Perception Following De-Epithelialized Free Gingival Graft Harvesting.

05/06/2020

1. Study Protocol 1. Objectives/Specific Aims:

The purpose of this study is to compare the effect of a hemostatic collagen sponge, a collagen sponge sealed with a bio-adhesive material, a Platelet rich fibrin and a physical barrier(stent) on the palatal donor sites with the purpose of minimizing postoperative pain after epithelialized gingival graft harvesting.

2. Materials and Method:

Study population:

A total of 80 patients seeking treatment at the UAB SOD Graduate Periodontology clinics will be recruited to participate in this study. The potential candidates will be approached during the treatment planning and/or pre-surgical visit in the periodontal clinic. The investigator/research staff will give the information sheet to the potential participants, explain the study and obtain the patient demographics if the patient participate in the study.

Conventional oral impressions will be made to fabricate a customized acrylic stent for the patient who will receive palatal stent.

This study will conduct a survey using the (VAS) Visual Analog Scale of the postoperative pain following the (FGG) Free Gingival Graft procedure technique with four different methods for coverage of the palatal donor site and evaluating differences in the patient painkiller consumption and willingness to repeat the surgery in the future. On the day of the surgical procedure participants will be given copies of a pain survey (Visual Analog Scale) to be filled every day for two weeks (14 days). The participants will receive a reminder phone call daily to complete the survey. The completed survey (VAS) forms will be collected/returned to the research staff on the day of their follow-up visit.

Study Group:

1: Collagen Plug + Sutures (CPS)

2: Collagen Plug with cyano-acrylate (CPC)

3: Platelet-rich Fibrin (PRF) + sutures

4: Palatal Stent (PS)

3. Study Background:

Periodontal plastic surgery has long been successfully performed for the treatment of gingival recessions and mucogingival deformities. Numerous techniques have been proposed in an attempt to obtain predictable root coverage outcomes. However, the results do not only depend on the technique selected but also on a variety of factors including but not limited to patient- and site-related factors.

Harris in 1997 developed a technique based on a special scalpel for including an epithelial margin into the harvested CTG. Years later, several variations for CTG harvesting were described aiming at reducing the postoperative morbidity by ensuring healing by primary intention. However, these techniques required a certain amount of palatal thickness in order to avoid desquamation of the undermined superficial flap due to compromised vascularization. Indeed, as highlighted by Zucchelli and colleagues, a common complication of these harvesting techniques is the

dehiscence or the necrosis of the primary flap if it was too thin or if sutures failed to secure it over the palatal wound.

To avoid the necrosis of the primary flap, a certain amount of the sub-epithelial connective tissue should be preserved and because of this, the deeper connective tissue harvested is less dense, less stable, richer in fatty and glandular tissue, and more prone to shrinkage. Some clinical studies have reported higher postoperative pain and morbidity following EGG when compared to CTG. Hence, several attempts were undertaken to control the palatal pain following EGG harvesting techniques, such as irradiating the palatal wound using lasers, the addition of platelet-rich fibrin, or a collagen matrix over the donor wound site. These techniques reported different levels of success. Recently, bio-adhesive materials, such as cyanoacrylate surgical glue, have been successfully introduced in ophthalmology, in the treatment of massive hemoptysis, in embolization, and for wound closure in dermatology due to their strong sealing, bacteriostatic, and hemostatic properties. Among the advantages of bioadhesive materials, their high tissue compatibility and long half-life have also been described.

This study will evaluate the postoperative pain following the EGG technique with four different methods for coverage of the palatal donor site. The control group will not be protected with any material. Test group 1 will be protected with Platelet rich Fibrin (PRF) while the test group 2 will consist of collagen protection with the additional layer of cyanoacrylate surgical glue. Test group 3 will consist of collagen protection with the application of a physical barrier (Stent) to cover the donor area.

4. Statistical Analysis

Patients' demographics and clinic characteristics at baseline will be summarize with descriptive statistics such as mean, standard deviation (SD), frequency, and proportion where appropriate. The group comparisons at baseline will be conducted with analysis of variance (ANOVA) or Fisher's exact test. Outcome variables – number of analgesics consumed and need for additional analgesics – will be summarize as median and range in each group and the group comparisons will be conducted with Kruskal-Wallis's test followed by post hoc Bonferroni-corrected Wilcoxon rank-sum tests. All the other outcome variables including pain score, swelling level, amount of bleeding, activity tolerance, and the need for additional analgesics will be summarize with mean \pm SD, and analyzed using a general linear mixed regression model to account for the repeated measures. Similar general linear mixed regression models will also use to explore the associations between outcome variables and graft length, width, area, and thickness. All analysis will be conducted using SAS 9.4 (Cary, NC, USA) under the significance level of 0.05.

Visual Analog Scale (VAS)

[figure not shown]
Subject ID #: _____

Site: _____

Date: _____

Please circle a number for each:

1. Pain

[figure not shown]
2. Swelling

[figure not shown]
3. Bleeding

4. Activity Tolerance Scale

5. Did you need to take more painkillers due to palatal pain? Total No. of pills: _____

6. Will you do this surgery again?

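### For the pairwise analgesic comparisons, Holm's step-down adjustment gives more power than the planned Bonferroni correction at the same error control and no cost

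*Combined protocol and SAP*

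**What the plan says.** Section 4 (Statistical Analysis) assigns two outcomes, "number of analgesics consumed and need for additional analgesics", to a rank-based comparison of the groups: a Kruskal-Wallis test and then "post hoc Bonferroni-corrected Wilcoxon rank-sum tests". All analyses are run "under the significance level of 0.05". No step-down method is named.

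The plan does not give the number of comparisons in the correction. It also does not say outright that the pairwise tests are run only when the Kruskal-Wallis test is significant, although the order of the sentence suggests it. Sections 2 and 3 refer to "four different methods for coverage of the palatal donor site", and the Study Group list in Section 2 has four entries. The sample is "A total of 80 patients", with no allocation stated.

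Pain, swelling, bleeding and activity tolerance go to a mixed model instead. The need for additional analgesics is listed under both methods.

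**The concern.** Single-step Bonferroni tests every comparison at the threshold needed if all the null hypotheses were true. Once one has been rejected, fewer can still be true, and the remaining comparisons could be tested less strictly without raising the family-wise error. Holm's procedure uses this fact; Bonferroni ignores it.

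The pairwise tests are where the trial would learn which coverings differ in painkiller use, one of the things Section 2 sets out to evaluate. With perhaps 20 patients per group, power for a single pair is modest, so an avoidable loss is worth removing. What is at stake is efficiency on the analgesic outcomes. The validity of the plan is not in question.

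**Working it through.** **Inputs.** From the documents: alpha 0.05, four groups, 80 patients. Assumed: two-sided tests, 80/4 = 20 per group, all pairs compared (4 × 3/2 = 6), and the effect sizes and distributions below. The plan gives no effect size, SD or power figure, so there is nothing of its own to reproduce.

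**Step 1: thresholds.** With m = 6, Bonferroni uses 0.05/6 = 0.00833 for every pair. Holm takes the p-values in increasing order and compares the i-th with 0.05/(m − i + 1), stopping at the first failure: 0.00833, 0.0100, 0.0125, 0.0167, 0.025, 0.05.

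**Step 2: Holm rejects all that Bonferroni rejects.** If k of the p-values are at most 0.05/m, they are the k smallest, and every Holm threshold is at least 0.05/m. So all k are rejected. This holds for any m.

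**Step 3: error control.** Suppose m0 nulls are true. The first true null in the ordering stands at position m − m0 + 1 or earlier, so its threshold is at most 0.05/m0. A false rejection therefore needs some true null with p ≤ 0.05/m0. The probability of that is at most m0 × 0.05/m0 = 0.05. No assumption beyond Bonferroni's is used.

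**Step 4: size of the gain.** Simulation used 20,000 trials per scenario, 20 per group and rank-sum tests with tie and continuity correction, with every procedure run only after a significant Kruskal-Wallis test. Pill counts are negative binomial with k = 1.5. Entries are percentages, Bonferroni / Holm.

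| Scenario | Average power per true difference | All true differences found | At least one found |
|---|---|---|---|
| Normal, one group shifted 0.8 SD | 35.4 / 38.5 | 13.2 / 18.5 | 59.8 / 59.9 |
| Normal, one group shifted 1.0 SD | 58.7 / 62.8 | 33.6 / 41.7 | 81.9 / 81.9 |
| Normal, one group shifted 1.2 SD | 79.1 / 82.8 | 59.5 / 67.8 | 94.6 / 94.6 |
| Normal, two groups shifted 1.0 SD | 59.0 / 65.4 | 24.6 / 36.5 | 89.8 / 89.8 |
| Counts, means 16, 8, 8, 8 | 29.4 / 31.6 | 11.9 / 15.7 | 49.0 / 49.1 |
| Counts, means 20, 8, 8, 8 | 56.0 / 59.2 | 35.0 / 41.5 | 76.2 / 76.2 |
| Counts, means 16, 16, 8, 8 | 29.5 / 32.5 | 5.1 / 9.5 | 61.4 / 61.4 |
| Normal, shifts 0, 0.4, 0.8, 1.2 SD | 28.5 / 31.9 | 0.0 / 0.0 | 84.5 / 84.5 |

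Average power rises by about 2 to 6 points. The chance of finding all true differences rises by about 4 to 12 points where three or four pairs differ. It stays near zero when all six differ. The chance of at least one finding is unchanged to within 0.1 point, because Holm's first threshold is also 0.05/6.

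Simulated family-wise error, Bonferroni / Holm: no differences (normal) 0.030 / 0.030; three equal groups and one 3 SD away 0.019 / 0.038; two equal pairs 3 SD apart 0.015 / 0.048.

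**Step 5: does the gate matter for Holm?** Barely. Without it, average power at 0.8 SD is 35.7 / 38.8 instead of 35.4 / 38.5.

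**Step 6: the optional extension.** Four groups can be all equal (6 true pairwise nulls), split 3+1 (3), 2+2 (2) or 2+1+1 (1), or all differ (0). After the Kruskal-Wallis test has rejected overall equality, at most three pairwise nulls can be true, which gives Shaffer's divisors 3, 3, 3, 3, 2, 1. Average power under this rule, in the table's row order, is 44.8, 68.5, 86.4, 69.4, 38.0, 66.0, 38.9 and 35.2: about 7 to 10 points above Bonferroni. Its family-wise error was 0.043 with no differences (normal), 0.044 with no differences (counts), and at most 0.048 in any scenario.

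**The case against.** **Bonferroni is not wrong.** It controls the family-wise error for any number of comparisons, and choosing a simple, conservative correction for post hoc tests is legitimate. This stands. A reader might infer that the plan contains an error, but it does not.

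**Six pairs at 0.0083 is an inference.** Section 3 also describes a control group and three test groups. If only contrasts with control were meant, Bonferroni would already test at 0.05/3 = 0.0167. Under that reading, a simulation in which the control differs from the other three gave ungated Bonferroni over three contrasts 47.8% average power at 0.8 SD, against 45.9% for the six-pair gated Shaffer rule (68.8% against 67.8% at 1.0 SD). So the larger gain depends on the family. Holm's advantage does not: Step 2 holds for three comparisons as for six, though its size would differ. The four coverings in Sections 1 and 2 make all pairs the more natural reading, but the plan should say so.

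**Gated Shaffer is not free.** It is tempting to claim its larger gain as costless. It is so only if the plan's pairwise tests are already conditional on the Kruskal-Wallis result, which Section 4 never states. Against ungated Bonferroni it loses a rejection in up to about 1% of trials. It also needs each pairwise null to be equality of distributions. If the rank-sum null is read as P(X > Y) = 1/2, that relation is not transitive and the limit of three true nulls fails. This objection stands, which is why Holm is the recommendation here.

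**The scope is narrow.** The stated purpose is to reduce postoperative pain, and pain is analysed by mixed model. This also stands.

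**Conclusion.** The point holds as a small, free improvement on the analgesic outcomes. That Holm is never worse than Bonferroni and has the same error control follows from Steps 2 and 3 and rests on no assumption about the trial. The size does rest on assumptions: 20 per group, all six pairs, and chosen effects and distributions. Under these, Holm adds about 2 to 6 points of average power per true difference and nothing material to the chance of finding at least one.

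The documents do not support a stronger conclusion. The planned analysis is valid, no pain result changes, and the gain of about 7 to 10 points from gated Shaffer is conditional on a gate and a null hypothesis that the plan has not specified.

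**What to change.** In Section 4, replace "post hoc Bonferroni-corrected Wilcoxon rank-sum tests" with *post hoc Wilcoxon rank-sum tests with Holm step-down adjustment*. State the family in the same sentence. If it is all six pairs within each outcome, the ordered thresholds are 0.05/6, 0.05/5, 0.05/4, 0.05/3, 0.05/2 and 0.05. Say whether the pairwise tests depend on a significant Kruskal-Wallis result.

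Optionally, if the plan makes the pairwise tests explicitly conditional on Kruskal-Wallis p ≤ 0.05 and defines the nulls as equality of distributions, the ordered thresholds may instead be 0.05/3 for the first four, then 0.05/2 and 0.05 (Shaffer).

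Either version costs a sentence of text and a few lines of SAS, with no extra patients or data. Holm loses no rejection that Bonferroni would make with the same gating. The Shaffer version carries the small loss described above if the present tests were meant to be ungated.

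### Graft size is analysed only in exploratory models, so the comparison of arms gives up possible precision and has no prespecified protection if wound size differs between arms

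*Combined protocol and SAP*

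**What the plan says.** Under 2. Materials and Method the plan gives the size of the study, "A total of 80 patients seeking treatment at the UAB SOD Graduate Periodontology clinics will be recruited to participate in this study", the comparison, "with four different methods for coverage of the palatal donor site", and the diary, "copies of a pain survey (Visual Analog Scale) to be filled every day for two weeks (14 days".

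Under 4. Statistical Analysis, pain, swelling, bleeding, activity tolerance and need for additional analgesics are to be "analyzed using a general linear mixed regression model to account for the repeated measures". No covariate is named for this model. Graft size appears once, in a further set of models: "Similar general linear mixed regression models will also use to explore the associations between outcome variables and graft length, width, area, and thickness".

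Balance between groups is addressed by tests: "The group comparisons at baseline will be conducted with analysis of variance (ANOVA") or Fisher's exact test. The text does not say whether graft size is among the characteristics tested, or what follows if groups differ.

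No section describes randomisation, stratification or limits on graft size, or says how and when grafts are measured. One sentence bears on the timing of assignment: "Conventional oral impressions will be made to fabricate a customized acrylic stent for the patient who will receive palatal stent".

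**The concern.** The coverings are meant to reduce pain from the palatal wound, and graft area and thickness describe that wound. The plan itself treats them as possible correlates of the outcomes, yet keeps them out of the comparison that answers the study question.

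Two things are at stake. If graft size predicts pain, the variation it explains stays in the error term of the arm comparison. And if one arm happens to have larger or thicker grafts, the plan does not say whether the comparison will allow for it. That decision, and the choice among four overlapping dimensions, could then be made after the data are seen. The second matters more here than in a trial with documented randomisation, because balance cannot be taken from the design as written.

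**Working it through.** The plan gives no power, effect size or SD, so there is no figure of its own to reproduce. What follows illustrates the size of the issue.

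**Inputs from the document.** 80 patients and four arms (section 2); tests "under the significance level of 0.05" (section 4); 14 daily scores (section 2).

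**Assumptions not in the document.** Equal arms, 80/4 = 20 each; two-sided tests; complete diaries; SD of a patient's mean pain over the 14 days set to 1; r, the within-arm correlation of graft size (area and thickness together) with that mean, shown from 0.1 to 0.5. With complete diaries, the day-averaged arm difference from a mixed model with arm, day, arm-by-day, area and thickness equals analysis of covariance on patient means. A simulated data set confirmed this (both −0.358, SE 0.281), so patient-level formulas apply.

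**Step 1: precision.** The unadjusted SE of a pairwise difference is √(2/20) = 0.316, on 80 − 4 = 76 df. Two covariates multiply the variance by (1 − r²) for what they explain and by about 1 + 2/73 for estimating them, where 73 = 80 − 4 − 2 − 1. This leaves 74 df. At r = 0.3 the multiplier is 0.91 × 1.0274 = 0.935; at r = 0.5 it is 0.75 × 1.0274 = 0.771. Detectable differences use the noncentral t distribution at 80% power.

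| r | Variance multiplier | Detectable difference (SD) | Power at 0.897 SD |
|---|---|---|---|
| unadjusted | 1 | 0.897 | 80% |
| 0.1 | 1.017 | 0.905 | 79% |
| 0.2 | 0.986 | 0.891 | 81% |
| 0.3 | 0.935 | 0.868 | 83% |
| 0.4 | 0.863 | 0.834 | 85% |
| 0.5 | 0.771 | 0.788 | 89% |

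Break-even is where (1 − r²)(75/73) = 1, so r² = 2/75 and r = 0.163.

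**Step 2: chance imbalance.** Under random allocation the standardised difference in graft size between two arms has SD 0.316. A given pair differs by at least 0.5 SD with probability P(|Z| ≥ 0.5/0.316) = 0.114; at least one of the six pairs does so with probability about 0.39.

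A difference of 0.5 SD shifts the unadjusted contrast by r × 0.5: 0.05, 0.15 or 0.25 SD at r = 0.1, 0.3 or 0.5. The test rejects beyond ±1.96 × 0.316 = ±0.620, while the SE given the imbalance is 0.316 × √(1 − r²). At r = 0.3 that SE is 0.302, so the false-positive rate is P(Z > (0.620 − 0.15)/0.302) + P(Z < (−0.620 − 0.15)/0.302) = 0.060 + 0.005 = 6.5%. The same formula gives 5.2% at r = 0.1 and 8.9% at r = 0.5. Simulation of the four-arm model gave 5.2%, 6.4% and 9.0%, against about 5% after adjustment.

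Better-balanced pairs offset this: with a 0.25 SD difference the formula gives 5.0%, 4.6% and 3.9%. Averaged over random allocations the unadjusted rate stays at 5%.

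**Step 3: the baseline test as a safeguard.** If graft size were among the characteristics tested, the four-group ANOVA (noncentral F, 3 and 76 df) would reach p < 0.05 with probability 32% when one arm is truly shifted by 0.5 SD, and 72% for 0.8 SD. It would often miss a shift large enough to matter.

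**The case against.** The strongest reply is that adjustment is a preference. The document gives no r. At 0.1 adjustment loses a little; at 0.2 and 0.3 the detectable difference moves only from 0.90 to 0.89 and 0.87 SD. A useful gain needs r of 0.4 to 0.5, which nothing in the plan supports. This stands as to size. It does not remove the case for prespecifying, which is cheap.

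A second reply concerns the remedy. The impressions for stent patients suggest that their assignment is known before harvest. If knowing the arm could affect how much tissue is taken, graft size is a post-assignment variable, and adjusting for it changes what the estimate means. This also stands, and it makes the choice of primary model conditional.

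Third, the exploratory models are called similar and may keep arm, which would already give a size-adjusted look. That is possible, but the plan does not rest its arm comparison on them.

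A reader might go further and infer that:

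- **The arm comparison is undefined** because arm, day and covariance terms are not named. An arm effect averaged over days is readily inferred from the stated aim. The unnamed terms are missing detail, not an error.
- **The unadjusted comparison is invalid, or allocation is non-random.** The document says neither. It is silent on allocation and nowhere says that graft size varies by arm. Early stent impressions do not show that it does.

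**Conclusion.** The point holds as a modest, inexpensive improvement to the analysis. The arm comparison forgoes whatever precision graft size could give and has no prespecified response to unequal wound size. With 20 per arm, the detectable difference would fall from 0.90 SD to 0.87 SD at r = 0.3 and to 0.79 SD at r = 0.5, with a slight loss below r of about 0.16. These sizes rest on equal arms, complete diaries, two-sided tests and an r that the document does not supply.

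Under random allocation the unadjusted comparison remains valid; what adjustment then adds is precision and protection against chance imbalance. If allocation is not random, adjustment deals only with measured, linearly modelled wound size. It cannot stand in for a description of how patients are allocated.

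**What to change.** 1. State when each arm is assigned relative to harvest, what determines graft size, and how, when and in whom grafts are measured.
2. In the mixed model for the arm comparison, prespecify graft area and graft thickness as covariates. Do not enter length, width and area together, since area is essentially the product of the other two. Name the pairwise arm difference averaged over the 14 days as the contrast. Arm, day, arm-by-day and the within-patient covariance can be written down in the same sentence.
3. Report the model without graft terms beside it. Make the adjusted model primary only if graft size is set by the recipient site or otherwise independently of the assigned covering. If the arm could influence graft size, keep the unadjusted model primary and read the adjusted estimate as the effect of the covering at a given wound size.
4. Do not let baseline p-values decide whether to adjust, and say how missing graft measurements are handled.

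The cost is a few sentences and two degrees of freedom. No new data are needed if graft dimensions are recorded for every patient, which the exploratory models imply but the text does not state; otherwise one set of measurements per graft. Comparisons made with the Kruskal-Wallis and Wilcoxon tests stay unadjusted.

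### Section 4 tests five or six outcomes, each at 0.05, without formally declaring pain primary, so the chance of at least one false-positive outcome is about 11–27%, depending on how the outcomes correlate

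*Combined protocol and SAP*

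**What the plan says.** Section 1 (Objectives/Specific Aims) compares four palatal coverings "with the purpose of minimizing postoperative pain after epithelialized gingival graft harvesting". Section 2 (Materials and Method) adds that the survey is also meant for "evaluating differences in the patient painkiller consumption and willingness to repeat the surgery in the future".

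Section 4 (Statistical Analysis) divides the outcomes between two methods:

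- "number of analgesics consumed and need for additional analgesics" are compared by "Kruskal-Wallis's test followed by post hoc Bonferroni-corrected Wilcoxon rank-sum tests".
- A general linear mixed model for repeated measures is used for "All the other outcome variables including pain score, swelling level, amount of bleeding, activity tolerance, and the need for additional analgesics".

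Need for additional analgesics is therefore assigned to both methods. Pain is listed in the second group alongside the others. The section closes with "All analysis will be conducted using SAS 9.4 (Cary, NC, USA) under the significance level of 0.05". No outcome is called primary or secondary, and no adjustment across outcomes is given. Only the graft-dimension associations are described as something to explore.

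**The concern.** The aim names one purpose, less pain, but the analysis section does not carry it through. Each outcome gets its own full 0.05, and nothing says beforehand which result answers the trial's question. The Bonferroni step does not help, because it adjusts the pairs of arms within an analgesic outcome and leaves the number of outcomes uncorrected.

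The stake is interpretation. If the coverings do not differ on pain, there is still a material chance that swelling, bleeding, activity tolerance or an analgesic outcome reaches 0.05 by chance. The plan gives no stated basis for treating that finding as less than a positive result for one covering.

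**Working it through.** **Plan's own figure.** The documents state no error rate across outcomes. The only error figure is the 0.05 level in Section 4, so there is nothing to reproduce.

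**Inputs.**

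- Level: 0.05 for every analysis (Section 4).
- Arms: four (Section 2, study groups; Section 3 also refers to "four different methods for coverage of the palatal donor site").
- Patients: 80 in total (Section 2). The allocation is not stated, so 20 per arm is assumed.
- Outcomes: six are named in Section 4, namely pain, swelling, bleeding, activity tolerance, number of analgesics and need for additional analgesics. Item 5 of the survey form asks about extra painkillers and the pill total together. If the two analgesic outcomes are one measurement, the count is five.
- Tests per outcome: one omnibus comparison of the arms. This is an assumption for the mixed models, since Section 4 does not say which effect is tested.
- Correlation between outcomes: not given, so varied from 0 to 0.9.

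**Step 1: independent outcomes.** The chance of at least one false positive among k tests is 1 − 0.95^k.

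- k = 5: 1 − 0.95^5 = 1 − 0.7738 = 22.6%
- k = 6: 1 − 0.95^6 = 1 − 0.7351 = 26.5%

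**Step 2: correlated outcomes.** Simulate four arms of 20 with no true differences. Each outcome is √ρ × (a patient-level term shared by all outcomes) + √(1 − ρ) × (a term of its own), so every pair of outcomes has correlation ρ. Test each outcome with the F test on 3 and 76 degrees of freedom at 0.05, and count the replicates with at least one rejection. With 200,000 replicates the simulation error is about 0.1 percentage point (√(0.22 × 0.78 / 200,000) = 0.0009).

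| Correlation | Five outcomes | Six outcomes |
|---|---|---|
| 0 | 22.5% | 26.2% |
| 0.5 | 18.9% | 21.6% |
| 0.7 | 15.7% | 17.5% |
| 0.9 | 10.8% | 11.3% |

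The first row agrees with Step 1. Rounded, the range is about 11% to 27%.

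**Step 3: what the stated correction does.** Four arms give 4 × 3 / 2 = 6 pairs, so Bonferroni tests each pair at 0.05 / 6 = 0.0083 within one Kruskal-Wallis outcome. The omnibus test of that outcome stays at 0.05, as do the tests of all other outcomes. The figures in Steps 1 and 2 do not change.

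**Step 4: if pain is read as primary anyway.** The non-pain outcomes number four or five. Under independence, the chance that at least one is falsely significant is 1 − 0.95^4 = 18.5% or 1 − 0.95^5 = 22.6%, and less with correlation. Inferring that pain is primary does not settle how those results are to be read.

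**Not counted.** The figures leave out separate tests for each of the 14 survey days, pairwise contrasts from the mixed models (for which no correction is stated), the second analysis of need for additional analgesics, and the graft-dimension models.

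**The case against.** The strongest reply is that pain is plainly the focus. The study title, the stated purpose and the closing paragraph of Section 3 (Study Background) all say so. That stands, and it rules out two stronger readings. A reader might infer that the plan has no discernible lead outcome; it does have one, and what is missing is the formal declaration in Section 4. A reader might also infer that a positive result on any outcome officially counts the same as one on pain. The documents do not say that: they give a significance level but no rule for success or for claiming superiority.

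A second reply concerns the count. A reader might add willingness to repeat the surgery as a seventh outcome and quote 1 − 0.95^7 = 30.2%. The documents do not support that as a headline. Section 4 names no test for willingness, and 30.2% needs seven mutually independent tests. That is implausible when the two analgesic outcomes appear to come from one form item and that item asks about painkillers taken because of palatal pain. The same dependence makes the upper end for six outcomes an upper limit rather than an expectation.

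A third reply is that a study of 80 patients built on a survey needs no formal adjustment of its secondary outcomes. As a matter of style, that is fair. Labelling them supportive and reporting estimates is as legitimate as a gated or Holm-adjusted family. It still requires the label, which Section 4 does not supply.

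**Conclusion.** The point holds as a gap between the aim and the analysis rule. Following Section 4 as written gives about an 11% to 27% chance of at least one falsely significant outcome when the coverings do not differ at all. The upper end is six independent outcomes; the lower end is five or six outcomes correlated at 0.9. Both the correlation and the single omnibus test per outcome are assumptions, because the documents specify neither. Across the whole range the rate is at least twice 5%, so the conclusion does not depend on where the true correlation lies. The stated focus on pain mitigates the problem, and the repair is cheap, so this is a change that should be made rather than a fatal defect.

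**What to change.** Extend the closing sentence of Section 4 to say:

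> Pain score is the only primary outcome. It is tested at the 0.05 level by one omnibus test from the mixed model, the overall group effect over the 14 daily scores. All other outcomes are secondary. Each is assigned one analysis and reported as a supportive estimate with a confidence interval; none can by itself establish that one covering is superior. Analyses of graft dimensions are exploratory.

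Three details matter:

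- **The pain test must be named.** The overall group effect is an example; a group-by-day test could be chosen instead, but only one can carry the 0.05. An omnibus test of four arms has no direction, so the text should not call it two-sided.
- **Each secondary outcome needs a single analysis.** Need for additional analgesics now has two and should keep one. If willingness to repeat the surgery is to be compared, it needs a named method.
- **Holm adjustment of the secondary outcomes is optional.** It is a matter of preference once they are labelled supportive.

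The error rate for the trial's one confirmatory claim is then 5%. The change needs no extra patients, visits or data. The cost is that a stand-alone significant secondary outcome can no longer be claimed as the trial's result.
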